To minimize the risk of a breach in confidentiality, unique codes will be used in place of participant names and all study staff will be trained in confidentiality. Personal health information will be coded and collected on password-protected mobile phones. All digital information will then be stored on an encrypted study computer. All paper records, including consent forms, will be stored in a locked filing cabinet at KDH. At the conclusion of the study period, all datasets for analysis will be de-identified and all identifiable information will be destroyed.

Adverse Event Reporting

A Data and Safety Monitoring Board (DSMB) will be designated to oversee the safety and effectiveness of the Aim 4 in this study. This committee will include one surgery expert, one global health delivery expert, one Rwandan health practitioner and one statistician. After seven months of accrual, we will compare rates of return between the three study arms. We anticipate 600 patients (200 per arm) will be included in this interim analysis. If the proportion who have returned in Arms 1 and 2 (intervention arms) is significantly lower compared to standard of care, then the study will be stopped or one study arm will be dropped. Further, if there are significantly more complex cases at return (higher rates of readmission or reoperation) in Arms 1 or 2, then the study will be stopped or one study arm will be dropped. The DSMB will meet once, immediately after the interim analysis, and the outcome of the DSMB review will be summarized in a letter to the IRBs of all participating institutions.

REFERENCES

2. World Health Organization. *Report on the Burden of Endemic Health Care-Associated Infection Worldwide*. 2011.

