With advances in mobile technology and telecommunications infrastructure in Rwanda, there is great potential to leverage mHealth strategies to support CHWs to identify SSI in the community and improve patient return to care. Here, we propose to optimize a simple screening protocol that can be implemented by CHWs with mHealth support to identify patients with SSI among surgical patients who return to the community following discharge from the hospital. We will then evaluate the impact of this intervention on appropriate return to care for patients with an SSI. We have previously piloted such strategies in rural Haiti where we found 85% agreement between the CHW diagnosis of SSI and the diagnosis of a surgeon.

Specific Aim 1: In order to determine whether or not the use of mHealth by CHWs improves the identification of SSI and timely return to care among surgical patients in rural Rwanda, we aim to optimize a simple screening protocol that can be implemented by lay CHWs in Rwanda that will help them to correctly identify SSI ten days post-surgery.

Specific Aim 2: We will assess the antibiotic prescribing practices during hospitalization and at discharge.

Specific Aim 3: We will describe water, sanitation and hygiene (WASH) resources at the hospital and at the mothers' homes.

Specific Aim 4: After optimizing the SSI screening protocol, we will compare the efficacy of the protocol across two groups: 1) patients who are visited by a surgical CHW who administers the protocol using a mobile phone 2) patients who receive a phone call from surgical CHWs who administer the protocol via phone. These groups will be compared to patients who receive the standard of care in Rwanda, which is no special follow-up after discharge.

Specific Aim 5: We aim to document process indicators measuring aspects of the CHW-mHealth intervention implementation. These measures will evaluate for successful and timely completion or compliance with each step of the specific aim 2.

Specific Aim 6: We will assess barriers to return to care, specifically in individuals in Arms 1 and 2 that receive follow-up and are recommended to return to care for suspected SSI, but fail to return to Kirehe District Hospital.

Specific Aim 7: We will determine standard post-operative follow-up care procedures for individuals who receive no additional follow-up (Arm 3).

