We will continue to consecutively enroll participants on post-operative day 2 from the adult female patient population receiving c-section surgery at KDH during a 14-month period. Randomization into the three study arms will take place at time of discharge. We will enroll 1092 participants in this phase of the study, 364 per study arm. Once enrolled, there will be no special retention strategies so as not to interfere with the outcomes under investigation in Aim 4 (return to care) or Aim 5 (process measures describing the CHW-mHealth intervention implementation). If the patient is still in the hospital 10 days following surgery, they will be excluded from the study given the inability to be randomized properly to the three arms of this phase. We will include patients from Mahama Refugee Camp when collecting information about the hospitalization and outcomes. However, these patients will not be asked to return for follow-up.

Sealed study packets, prepared in advance, will be available at KDH. Each study packet will have the arm assignment for the patient, which will be randomly assigned during the preparation of the materials using a random number generator. Both the research staff and the patient will be unaware of the arm assignment during the consent process and the assignment will be revealed only after the patient has agreed to participate. In this phase, no participants will receive travel vouchers, to ensure appropriate comparison between the intervention and standard of care groups. Per standard of care, all patients will receive information on the signs of SSI and will be instructed to return as soon as any of these present. (Appendix A).

STUDY PROCEDURES:

This research includes two distinct phases. During the first phase, we will optimize the SSI screening protocol by piloting it among a cross-section of patients receiving surgery at KDH, Rwanda. In the second phase, we will randomize patients receiving surgery at KDH to one of three arms – standard of care and the two intervention arms. At the conclusion of the study, we will compare rates of return and severity of SSI at return among the three arms and report process indicators describing the implementation of the CHW-mHealth interventions in the two intervention arms. In this study, patients will be assessed at 10 days after their operation, as symptoms for SSI usually develop during the first 6-9 post-operative days.²³

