Patients in Arms 1 and 2, who are determined by the sCHW to have a suspected SSI and referred back to care, but fail to return back to care within one week will be identified. Data collectors will return to these patients' homes at 22-30 days post-operation to interview them on why they failed to return to care. The interviews will be semi-structured, including questions on established barriers to care and allowing for open-ended response. A random sample of patients in Arm 3 will be visited at home at 22-30 days post-operation by data collectors who will

interview them on their follow-up care procedures. The interviews will be semi-structured, including questions on standard care paths and allowing for open-ended response.

For a subset of 50 patients, we will administer at discharge a Financial Risk Protection Survey (Appendix D), an existing validated tool, to understand the total costs of care and the costs relative to normal household expenditures.

Analysis and Outcomes:

Aim 4:

For Aim 4, we will compare the proportion of patients who return for follow-up with an SSI in Arms 1 and 2 to Arm 3 (standard of care) using a two-sided, two-sample test of proportions at the $\alpha=0.05$ significance level. We will use a logistic regression model to assess the impact of study arm on measures of severity at presentation (for example, readmission to hospital), controlling for potential confounders collected at enrollment. All analyses will be completed as intention to treat, regardless of whether the patient had contact with the sCHW or was screened by the mHealth tool in Arms 1 and 2. For Aim 4, for Arms 1 and 2, we will report percent for each of the process measures (for example, percent of home visits or calls completed on time) with 95% confidence intervals. We will assess the impact of study arm on measures of severity at presentation, controlling for potential confounders collected at enrollment. We will describe standard of care patient follow-up behavior using results from Arm 3. We will also report surgery-related reasons for return to care beyond SSI. We will perform a sensitivity analysis to determine under what range of SSI rates the results are still valid.

Aim 5:

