The sample size for Phase 2 of this study was driven by Aim 4. We assume that the rates of SSI in the three arms will be similar (due to randomization), and we anticipate more patients with SSI will return to care in Arms 1 and 2 than in Arm 3. In each arm, we will enroll 364 patients. Assuming a 15% SSI rate, this translates to 55 SSI cases per arm. In Arm 3, we expect approximately 6% of all surgical patients to return with an SSI corresponding to 40% of all SSI infections. In Arms 1 and 2, we hypothesize twice as many patients with SSI (80%, n=44) will return. We would have an 81% power to detect a difference between the rate of patients that returned with SSI in Arms 1 and 2 (12%) as compared to Arm 3 (6%) with a two-sided test at the $\alpha=0.05$ significance level (Table 1).

	Arm 1	Arm 2	Arm 3
Description	Home visit on 10 th post-operative day (± 3 days)	Phone call on 10 th post-operative day (± 3 days)	Standard of care
Number per arm	364	364	364
Anticipated number with SSI	55	55	55
Hypothesized number to return with SSI days 7-14	44 (80%)	44 (80%)	22 (40%)
Overall hypothesized proportion that	0.12	0.12	0.06

will return on POD 7-14 with SSI			
--	--	--	--

RISKS AND DISCOMFORTS:

The study does not alter the standard of care in any way that increases risk to the patient. Risks to privacy are minimized by accessing data on password protected mobile phones, storing data on HIPAA-compliant servers, and de-identifying the database as soon as is practicable after the conclusion of the study period.

The primary risk associated with participation in this study is a breach in confidentiality, resulting in the disclosure of patient information. This risk is considered minimal; as unique codes will be used in place of participant names. All study staff will be trained in confidentiality. To further reduce the likelihood of a breach in confidentiality, all digital information will be stored in a password-protected document on an encrypted study computer, and all paper records will be stored in a locked file cabinet in a secure room at KDH.

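### A woman whose SSI was diagnosed before discharge can be randomised and counted in Aim 4, which dilutes the contrast; the 55 cases per arm and 81% power probably overstate what the intervention can act on

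*Combined protocol and SAP*

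**What the plan says.** The Specific Aims describe a screening protocol meant "to identify patients with SSI among surgical patients who return to the community following discharge from the hospital".

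Phase 2 (Subject Selection and Enrollment) enrols without regard to wound status: "We will continue to consecutively enroll participants on post-operative day 2 from the adult female patient population receiving c-section surgery at KDH". On timing it says "Randomization into the three study arms will take place at time of discharge". The exclusion linked to the hospital course is "If the patient is still in the hospital 10 days following surgery, they will be excluded from the study"; the Phase 2 analysis section repeats it for the assigned screening day. Neither place mentions a woman whose SSI was diagnosed before she left.

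For Aim 4 the plan will "compare the proportion of patients who return for follow-up with an SSI in Arms 1 and 2 to Arm 3 (standard of care". The outcome comes from a tracker log and from the presence of an SSI recorded in the chart. No rule separates an SSI known at discharge from a new one.

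Study Procedures states that "symptoms for SSI usually develop during the first 6-9 post-operative days". The Power Analysis says: "Assuming a 15% SSI rate, this translates to 55 SSI cases per arm". It then applies 80% return (Arms 1 and 2) and 40% return (Arm 3) to all of those cases.

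**The concern.** With onset usually on post-operative days 6 to 9 and a cut-off at day 10, there is an interval in which an SSI can be diagnosed in hospital and the woman then discharged and randomised. Her infection is already known, so the screen by the surgical community health worker (sCHW) cannot alter whether it is found. If she comes back with it at a rate unrelated to arm, she adds similar counts to all three arms. The absolute difference shrinks, and the result answers the question about infections found in the community less cleanly.

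The power calculation has a related weakness. The 15% lies within the 10-20% that the plan expects for patients having surgery at the hospital, and Phase 1 calls it an overall rate. Phase 2 uses it unchanged, although it drops day-10 inpatients and its intervention acts only after discharge. The planned power is only just above 80%, so a modest overstatement matters.

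**Working it through.** **Inputs from the documents.** 364 per arm; two-sided alpha 0.05; SSI rate 15%; return with SSI 80% of cases in Arms 1 and 2 and 40% in Arm 3 (Power Analysis, Table 1).

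**Assumed, because the documents do not give them.** f is the share of the 15% diagnosed in the index stay in women who then leave before day 10. q is the share of those women counted as returning with that SSI, taken as equal in all arms.

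**1. Reproduce the stated power.** Each arm has 364 x 0.15 = 54.6, about 55 cases. The rates are 0.15 x 0.8 = 12% and 0.15 x 0.4 = 6%. For one intervention arm against Arm 3, by the normal approximation with pooled variance under the null:

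Power = Φ{[|p1 − p3| − 1.96 √(2p̄(1 − p̄)/n)] / √([p1(1 − p1) + p3(1 − p3)]/n)}

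With p̄ = 0.09 and n = 364 this is Φ{(0.06 − 0.0416)/0.0211} = Φ(0.873) = 80.9%. The stated 81% reproduces.

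**2. Known SSI kept in the trial, as part of the 15%.**

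p1 = 0.15[0.8(1 − f) + fq]; p3 = 0.15[0.4(1 − f) + fq]; difference = 0.06(1 − f).

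Example, f = 10% and q = 80%: p1 = 0.15(0.72 + 0.08) = 12.0%; p3 = 0.15(0.36 + 0.08) = 6.6%; power 70.9%.

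**3. Known SSI not randomised, replaced to keep 364 per arm.** The SSI rate among those left is 0.15(1 − f)/(1 − 0.15f). At f = 10% it is 0.135/0.985 = 13.7%, giving 11.0% v 5.5% and power 76.9%.

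| f | No change, q = 0 | No change, q = 80% | Excluded and replaced |
|---|---|---|---|
| 5% | 11.4% v 5.7%, power 78.6% | 12.0% v 6.3%, power 76.1% | 11.5% v 5.7%, power 79.0% |
| 10% | 10.8% v 5.4%, power 76.2% | 12.0% v 6.6%, power 70.9% | 11.0% v 5.5%, power 76.9% |
| 20% | 9.6% v 4.8%, power 70.8% | 12.0% v 7.2%, power 59.4% | 9.9% v 4.9%, power 72.2% |

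The q = 0 column also gives the power if these women stay in but only SSI first diagnosed after discharge is counted. The gain from exclusion, as q goes from 0 to 80%, is 0.4 to 2.9 points at f = 5%, 0.7 to 6.0 at f = 10%, and 1.4 to 12.8 at f = 20%.

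**4. The other reading: 15% is already the rate after discharge, and known SSI comes on top in a share g of women.** Then p1 = 0.12(1 − g) + gq and p3 = 0.06(1 − g) + gq. For q from 0 to 80%, power is 80.4% to 77.3% at g = 1%, 80.0% to 73.9% at g = 2%, and 79.6% to 70.5% at g = 3%. Exclusion with replacement returns it to 80.9%.

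**5. What the 15% seems to cover.** Phase 1 expects 525 x 0.9 x 0.15 = 71 cases, so the rate is applied to everyone followed up. The Phase 1 procedures include women not yet discharged at the day-10 visit. Phase 2 excludes that group. The effect of dropping them is not modelled above.

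**The case against.** The strongest reply is that Aim 4 measures return to care with an SSI, not first detection. An sCHW who visits or phones a woman with a persistent SSI refers her back, so the intervention may change her return too. This stands. A reader might infer that the intervention can do nothing for these women; the documents do not support that. Equal return across arms is an assumption, and dilution follows only as far as it holds.

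Second, the group may be small. The woman must be diagnosed in hospital, leave before day 10 and return still infected, and Table 1 counts returns on days 7 to 14. The background says that SSI in such settings often appears after discharge, and no usual discharge day is given. If discharge is early, f may be small. This also stands, and it is why a range is shown.

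Third, a reader might take the 12.8-point gain at f = 20% and q = 80% as the benefit of excluding these women. It is one corner of the range. An 80% return in Arm 3 would be twice the plan's own 40%, and at q = 0 the gain at f = 20% is 1.4 points.

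Fourth, Aim 4 includes a sensitivity analysis over SSI rates. That partly covers uncertainty in the 15%, but nothing says that it will separate SSI known before discharge from SSI arising later.

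Finally, keeping every discharged woman fits the long-term goal of offering the intervention to all surgical patients. That is a legitimate choice, but the plan does not state it for women with a known SSI. That they count is inferred from silence.

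**Conclusion.** The gap is real and worth closing: neither eligibility nor the endpoint deals with an SSI known at randomisation, and as worded the endpoint would count it. The consequence is dilution and a less clear answer about SSI found after return home. A reader might infer bias between arms; randomisation at discharge balances these women in expectation, so that does not follow.

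The size is not known. If the 15% covers all SSI, power with no change is about 79% to 76% at f = 5%, 76% to 71% at f = 10% and 71% to 59% at f = 20%, for q from 0 to 80%. Excluding and replacing gives 79%, 77% and 72%. Exclusion alone therefore does not restore 81%; part of the loss comes from applying an overall rate to a population followed after discharge. The 55 cases and 81% are probably optimistic, but they hold after exclusion if the 15% already means SSI arising after discharge. The documents do not settle which is meant.

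**What to change.** Choose one rule and write it into Phase 2 before data are seen:

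- At discharge, before the packet is opened, check the chart and do not randomise a woman with an SSI already diagnosed in the index stay; or
- keep her, record her SSI status at discharge, and count in Aim 4 only an SSI first diagnosed after discharge.

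State whether the same rule applies to the severity analysis and to the interim comparison for the DSMB.

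Restate the 15%, the 55 cases and the 81% for women discharged before day 10 without an SSI. Phase 1 can supply the rate: it records documented complications, whether the woman is still admitted at the visit, and the GP diagnosis, all in the same hospital.

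The cost is small. A few consenting women are not randomised, and the stated power becomes somewhat lower. The timing of the chart check must be fixed: Study Procedures describes chart extraction alongside the discharge survey, but Data Safety puts it at enrolment or after the return visit. Enrolment is on day 2, before the usual onset of symptoms, so extraction then would miss most of these infections.

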All consenting participants will have basic demographic and socioeconomic data collected by self-report via a survey administered by the study data collector at time of discharge. The study data collector will extract additional clinical data from the patient file. At time of discharge, participants will receive surgery follow-up instructions (Appendix A), including a set of warning signs for SSI and when to return to a health center, per standard of care. Additional human subjects contact will depend on study arm assignment. Individuals in Arm 1 will be visited at home by the sCHW who will administer the optimized SSI protocol via the mHealth device. Following the screening, the sCHWs will use the cell phone to photograph the surgical wound and record the GPS location of the visit. Individuals in Arm 2 will be phoned by the sCHW who will administer the SSI protocol over the phone. Individuals in Arm 3 will not have any additional contact beyond standard of care (Figure 1).

Figure 1:

BIOSTATISTICAL AND QUALITATIVE ANALYSIS:

Phase 1:

At the time of enrollment, study staff will administer a basic survey to record self-reported data on patient demographics (gender, age, weight, height, education level, location of residence, distance to hospital) and socioeconomic status (monthly household income, land ownership, cost of transport as a barrier to receiving health care). Study staff will also extract data from clinical charts on past medical history, type of surgery, time from surgery recommendation to operation, pre-operative antibiotic use/time, wound class, and any documented surgical complications. Clinical information will continue to be collected up to 90 days for any patients who are never discharged or for any patient who is readmitted for a surgical complication. For patients that are transferred to Kigali for tertiary care, we will use data collected routinely collected by the Right to Health Care program to complete their follow up information.

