Basic demographic and clinical data will be recorded at baseline by study staff, as described in phase 1. For Arms 1 and 2, addresses/phone numbers and availability will be documented for patient follow-up. At ten post-operative days (± 3 days), sCHWs will visit patients in Arm 1 at the address provided. The sCHW will be assisted by a local village CHW to identify the patients' homes. Once there, the sCHW will administer the SSI screening protocol with prompting from the phone, record responses into the phone, take a photo of the wound, and take GPS coordinates. Patients in Arm 2 will be phoned by the sCHW on the tenth post-operative day (± 3 days). The sCHW will administer the SSI screening protocol over the phone, prompted by the smartphone application to ask the appropriate questions. For both arms, patients identified as having an SSI will be referred back to KDH for care. These patients will also be asked a set of questions to assess for possible barriers to return of follow up. In this phase, patients will not receive financial support to return to the clinic. Patients not identified with SSI will be reminded of the warning signs and follow-up instructions. Patients still hospitalized at the hospitalized on their assigned screening day will be excluded from the study as they will not be eligible for the expected study follow up.

A patient tracker log at the hospital will be used to document patient return for follow-up care. The log will also document patients that self-present with potential SSI. Study staff will extract from the clinical chart the presence of an SSI, severity, treatment obtained, need for operative intervention, hospitalization, and/ or complications as recorded by a KDH GP. During the study period, clinical charts will be audited for completeness and GPs will be trained in data quality to ensure the accuracy of this clinical data. In addition, study staff will track process measures related to Arms 1 and 2.

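### Aim 4 return is recorded only at Kirehe District Hospital, while discharge advice speaks of a health center and only Arms 1 and 2 are later referred to the hospital, so the effect on return to care may be inflated

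*Combined protocol and SAP*

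**What the plan says.** The combined protocol and SAP describes the place of care in three ways.

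- **Study Procedures, Phase 2.** All participants receive discharge instructions, "including a set of warning signs for SSI and when to return to a health center, per standard of care". For the control arm, "Individuals in Arm 3 will not have any additional contact beyond standard of care".
- **Subject Selection and Enrollment, Phase 2.** The same advice, citing the same Appendix A, names no facility: "all patients will receive information on the signs of SSI and will be instructed to return as soon as any of these present".
- **Biostatistical and Qualitative Analysis, Phase 2.** "For both arms, patients identified as having an SSI will be referred back to KDH for care". Arm 3 has no equivalent step.

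Recording happens in one place. "A patient tracker log at the hospital will be used to document patient return for follow-up care". Women who come back unprompted with a possible infection are entered in that same hospital record. SSI status and severity are taken from the chart as entered by a KDH general practitioner. No section describes capture of health-center visits for Aim 4.

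The endpoint in Analysis and Outcomes, Aim 4, is the proportion who return for follow-up with an SSI, with no facility stated. The overall aim is timely return to care, and the Power Analysis uses the same broad terms: "we anticipate more patients with SSI will return to care in Arms 1 and 2 than in Arm 3". Only Aim 6 words failure to return as failure to return to KDH.

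A random sample of Arm 3, of unstated size, is interviewed at home on days 22-30 about follow-up care. The answers are used descriptively.

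**The concern.** Assignment can change where a woman takes an infected wound, and the endpoint sees only one of those places. An Arm 3 woman who acts on the discharge advice and is treated at a health center is scored as not returning. A woman with the same infection in Arm 1 or 2 who screens positive is sent to the facility that keeps the log. The intervention could then appear to succeed by moving visits from health centers to KDH, without more infected women reaching care. Randomization and intention-to-treat analysis do not remove this, because the difference arises after assignment and in the measurement.

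The interim review is also exposed. Under Adverse Event Reporting, the study may be stopped or an arm dropped if return in Arms 1 and 2 is significantly lower than under standard of care. If the Arm 3 rate is understated more than the others, a real reduction in return to care is harder to see.

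The planned sensitivity analysis over SSI rates does not cover this, since it varies how many infections occur and not where they are treated.

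**Working it through.** **Inputs (Power Analysis; Aim 4).** 364 per arm; SSI rate 15%; return with SSI 12% in Arms 1 and 2 (80% of SSI cases) and 6% in Arm 3 (40%); two-sided test of two proportions, alpha 0.05; stated power 81%. The documents give no share of SSI care at health centers, so every such share below is an assumption.

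**Step 1: reproduce the plan's figure.** Pooled SE = √(2 × 0.09 × 0.91 / 364) = 0.0212. Unpooled SE = √((0.12 × 0.88 + 0.06 × 0.94) / 364) = 0.0211. Power = Φ((0.06 − 1.96 × 0.0212) / 0.0211) = Φ(0.87) = 81%. The stated figure is correct for one intervention arm against Arm 3.

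**Step 2: size of the bias.** Let h3 and h1 be the shares of SSI cases treated only at a health center in Arm 3 and in an intervention arm. Then

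logged difference − true any-facility difference = 0.15 × (h3 − h1).

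Each 10-point excess adds 0.15 × 0.10 = 1.5 points. With logged rates of 12% and 6%, and h1 = 0:

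| h3 | True Arm 3 rate | True difference | True ratio |
|---|---|---|---|
| 0% | 6.0% | 6.0 points | 2.00 |
| 10% | 7.5% | 4.5 points | 1.60 |
| 20% | 9.0% | 3.0 points | 1.33 |
| 30% | 10.5% | 1.5 points | 1.14 |
| 40% | 12.0% | 0 points | 1.00 |

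If h1 = h3, this term adds nothing to the absolute difference.

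**Step 3: tipping point if the trial logs exactly 12% and 6%.** The lower 95% limit is 0.06 − 1.96 × 0.0211 = 0.0186. It reaches zero at an excess of 0.0186 / 0.15, about 12 percentage points of SSI cases. The estimate itself reaches zero at 0.06 / 0.15 = 40 points. This treats the shift and the 15% rate as known.

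**Step 4: chance of a significant result with no true effect.** Let c be the true return to any facility, equal in all arms, and s the share of those visits that go only to a health center. Logged rates are c(1 − s3) in Arm 3 and c(1 − s1) in an intervention arm. The test is that of Step 1, counting both tails.

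| Assumption | s3 = 25% | s3 = 33% | s3 = 50% |
|---|---|---|---|
| c = 12%, s1 = 0 (worst case) | 26% | 43% | 81% |
| c = 12%, s1 = half of s3 | 10% | 15% | 34% |
| c = 6%, s1 = 0 | 15% | 23% | 50% |
| c = 6%, s1 = half of s3 | 8% | 10% | 19% |

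Worst case at 50%: 0.12 × 0.5 = 6% against 12%, the planned contrast exactly. Since 12% is 80% of SSI cases, half of those visits is 40% of cases, which agrees with Step 2. Mildest row at 50%: 0.06 × 0.75 = 4.5% against 0.06 × 0.5 = 3.0%.

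**The case against.** **The endpoint may simply be return to KDH.** Aim 6 words failure that way, the log and charts are KDH's, and the 6% assumed for Arm 3 is close to the 7.3% of obstetric surgical patients whom the preliminary chart review found had returned to the hospital with an SSI. On that reading nobody is misclassified and the power calculation fits its endpoint. This stands as far as it goes. But Aim 4 does not say so, and the stated aim and the Power Analysis speak of return to care. The remaining defect is then an undefined endpoint with too broad a conclusion.

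**The destination rests on one phrase.** Appendix A, which holds the actual instructions, is not in the text available, and facility terms are used loosely elsewhere (the clinic, the hospital, KDH). A reader might infer that Arm 3 is steered away from KDH. The documents show only that the sections differ.

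**Arms 1 and 2 receive the same discharge advice.** Symptoms are said usually to develop on days 6-9, and contact is at day 10 ± 3, so some of these women may already have gone to a health center. Those never reached, and those who screen negative and worsen later, are also unlogged if treated there. Only the Arm 3 excess biases the difference. This stands, and it is why the 26%, 43% and 81% figures are a worst case.

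**Health centers may send SSI cases on to KDH**, where they would be logged. The documents do not say.

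**Aim 4 does use Arm 3 follow-up data.** It includes a description of standard-of-care follow-up behavior. That is so, but it leaves the between-arm comparison unchanged.

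**Conclusion.** The concern holds as a risk that the plan leaves open. Return and SSI status are recorded at KDH only, and only screen-positive women in Arms 1 and 2 are referred there. As a measure of return to care, the Aim 4 difference may therefore be inflated in favor of the intervention, and the interim check for lower return may be weakened.

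The size is unknown. At the plan's 15% SSI rate it is 1.5 points per 10-point excess of health-center-only treatment in Arm 3, against a planned 6 points. With no true effect, the chance of a significant result runs from about 8% to 81% over the assumptions in Step 4. The upper end needs half of Arm 3 SSI visits diverted, none in Arms 1 and 2, and 80% of Arm 3 SSI cases reaching care somewhere, whereas the plan expects 40% of them to return.

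A reader might go further and conclude that the effect is inflated, or that the 81% power is wrong. The documents support neither. They give no health-center share and no rule on onward referral, and the power figure reproduces and suits a KDH-return endpoint.

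**What to change.** 1. Reconcile Subject Selection and Enrollment, Study Procedures, and the Phase 2 analysis section (with Appendix A) on where women are told to go. Which destination is right is for the study team to decide.
2. Define the Aim 4 endpoint as return to KDH with an SSI, and limit the Aim 4 conclusion to return to KDH, not return to care in general.
3. Pre-specify a tipping-point analysis over h3 − h1, the Arm 3 minus intervention-arm difference in the share of SSI cases treated only at a health center. Report the excess at which the lower confidence limit, and then the estimate, reaches zero. To judge which values of h3 are plausible, add one question to the planned Arm 3 interviews on days 22-30: whether care for the wound was sought at any facility, where and when. These interviews fall after the day 7-14 return window in the Power Analysis table, so they should not affect return within it.

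Do not build a corrected between-arm estimate from answers around day 10 in Arms 1 and 2 and answers on days 22-30 in Arm 3. Later health-center care would be counted in Arm 3 and largely missed in the others, which would tend to bias against the intervention. Any direct comparison needs the same question and the same window in all three arms.

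The cost is one question on an existing contact and one added analysis. The headline claim narrows to KDH. The health-center data will be self-reported, will not be SSI diagnoses recorded by a general practitioner, and come from a sample of unstated size, so they will be imprecise.
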